#### **D.5. Randomized Control Trial of the BI, Messaging, and Website Extenders (Aim 3) [Months 13 – 24]**

**a. Overview.** We plan a pilot study to assess the feasibility and acceptability of the BI and website, to obtain preliminary evidence of BI efficacy (on alcohol use and sex behavior outcomes), and to determine feasibility of procedures (e.g., enrollment, BI and website exposure, follow-up rates) for a future RCT.

**b. Design.** We plan a 2 (interventions) x 2 (baseline, follow-up) design. Women will be randomized, complete baseline, receive intervention (BI or brochure), post-survey (BI arm only), and 3-month follow-up. Measures will assess IMB constructs, alcohol, and sexual behavior, and STIs. Rationale for control: We chose a brochure because it is a science-based (CDC and NIAAA material) alternative that is representative of what clinics currently provide.

**c. Sample** ( $n=50$ ) was based on published guidelines for treatment development research, which recommend 15-30 per cell for Phase IB research. This also aligns with NIH expectations for R34 research. We recognize that the trial is not adequately powered to detect between-group differences, but it can clarify the potential of the intervention and suggest effect sizes (ES). We also know that ES estimates will have large standard errors. We primarily aim to find a pattern of results that is supportive of the experimental treatment.

**d. Participants.** We will recruit 50 women using screening, eligibility, recruitment, and consent procedures described in D.1.c. Women who participated in Aim 1 or 2 will not be eligible.

**e. Baseline.** Participants will complete the CASI on a tablet computer. Measures included in the CASI are listed in Table 2; the measures are reliable and valid, and have been used in prior research with young women. The CASI will take ~45 mins, and will assess background variables, outcomes, mediators, and moderators.

The self-report **outcomes** include sexual behavior; alcohol use; and the co-occurrence of sex and alcohol.

Consistent with PA-13-078, we will assess hypothesized **mediators** and **moderators**. We recognize that we will not have sufficient statistical power to test mediation or moderation in this pilot. However, we will evaluate short-term intervention effects on the hypothesized intervening variables, to determine if they have promise as potential mediators for a subsequent RCT.

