To determine **feasibility** of the BI and of an RCT, we will calculate the percentage of individuals who were: eligible; consented; attended their intervention; accessed the website; and returned for the follow-up. Based on previous research, we expect  $\geq 90\%$  of those assigned to a BI to attend their intervention. Based on our recent trials (R01-MH068171), we expect  $\geq 80\%$  of all women to return for the 3-month follow-up.

To determine **acceptability** of the BI, messaging and website, we will calculate Ms for the satisfaction surveys, and inspect responses. We **predict** that the intervention materials will be well-accepted, as shown by mean ratings  $\geq 4$  on a 5-point Likert scale. To further evaluate the **acceptability** of the messaging and website, we will collect use metrics (e.g., timing and frequency of website access, number of clicks on links for information, video view time). We **predict**, and will construe as acceptable, if women receive messages, link to the website, and view videos all the way through/multiple times.

To obtain preliminary evidence of BI **efficacy**, repeated measures ANOVAs will test intervention and time effects on the primary outcomes (alcohol use frequency, quantity, binge frequency; condom use, number of sexual partners; alcohol use before sex). We **hypothesize** an intervention x time interaction for all outcomes; thus, we **hypothesize** that BI recipients but not controls will reduce alcohol use and alcohol use before sex, increase proportion of protected sex, reduce condom use problems and number of partners.

To prepare for a future trial, we also provide preliminary data on mechanisms of action by testing intervention effects on **hypothesized mediators** (e.g., IMB constructs, attitudes, norms, self-efficacy).

**j. Effect sizes and power.** We recognize that effect size estimates based on small samples often have large SDs and wide confidence intervals (CIs). We also acknowledge that we will not have power to detect statistically significant results. Nonetheless, pilot data are useful to gauge whether BI effects are encouraging, to examine distribution of outcome variables, to inform future analytic approaches, and to suggest the range of effect sizes that are reasonable to expect in a future trial. Thus, the focus of our analyses will not be on strict significance testing but on estimating effect sizes and CIs.

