## Data Analyses Plan

For the feasibility data, we produced a Consort flow figure and calculated summary statistics to report the findings. For the acceptability data, we calculated summary statistics and identified illustrative quotes from the semi-structured interviews. Prior to analyzing the efficacy data, we used t-test and chi-square analyses to determine if randomization produced equivalent groups with respect to demographic characteristics and outcome measures.

For the efficacy data, we used inferential statistics to compare the two conditions to one another. Specifically, we used generalized estimating equations (GEE; Hardin & Hilbe, 2013) to examine the impact of the intervention on primary outcomes (i.e., typical drinks per week, maximum drinks per day, number of heavy episodic drinking days, alcohol-related consequences, number of sexual partners, and alcohol use before sex) as well as to model change over time. We used an intent-to-treat approach such that data from all women were used. We hypothesized an intervention-by-time interaction such that participants in the BI, but not the control, condition would reduce alcohol use and sex risk behavior over time. All analyses examined the impact of time (baseline vs. follow-up), intervention condition (control vs. BI), and the time-by-condition interaction controlling for age. When interactions were not significant, models were run without the interaction terms. Count variables (i.e., drinks per week, maximum drinks per day, heavy episodic drinking days, number of partners, drinks before sex) were analyzed using a Poisson distribution unless otherwise indicated. Alcohol consequences were analyzed using linear models.

For condomless sex, a GEE model could not be fit due to significant over-dispersion bounded by a large number of zeroes. Instead, a zero-inflated negative binomial model was chosen based on the (a) lower AIC and BIC values in the negative binomial versus Poisson models, and zero-inflated versus non-inflated models; and the (b) likelihood ratio test comparing zero-inflated Poisson and negative binomial models (lr test:  $\chi^2(1) = 60.76, p < .001$ ) (Long & Freese, 2006). Further, a zero-inflated model is considered particularly appropriate for sexual health research, such as condomless sex (He, Tang, Wang, & Crits-Cristoph, 2014), given that some mechanisms responsible for zero counts in the data differ from

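### For the GEE outcomes the BI effect is a difference in change that makes inefficient use of baseline, and when the interaction is dropped it is no longer a 3-month effect

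*SAP*

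**What the plan says.** The SAP (Data Analyses Plan) gives one model structure for efficacy: "All analyses examined the impact of time (baseline vs. follow-up), intervention condition (control vs. BI), and the time-by-condition interaction controlling for age". It names GEE for six primary outcomes: drinks per week, maximum drinks per day, heavy drinking days, alcohol consequences, partners, and alcohol before sex. A further rule follows: "When interactions were not significant, models were run without the interaction terms". Condomless sex has its own zero-inflated negative binomial model, and the SAP does not say how baseline enters it. Apart from its role as an outcome row, the baseline value is used only in t-tests and chi-square tests of group equivalence.

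The protocol targets the same contrast. In D.5.i, "repeated measures ANOVAs will test intervention and time effects on the primary outcomes", with an intervention-by-time interaction hypothesised. In D.5.j, "the focus of our analyses will not be on strict significance testing but on estimating effect sizes and CIs". The same section concedes that the trial lacks power for significance.

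**The concern.** With condition as a free term, the model lets the arms differ at baseline and subtracts that whole gap from the follow-up difference. Randomisation makes the expected gap zero, and only part of a chance gap persists to month 3. Subtracting all of it adds noise. Where the deliverable is an effect size with its CI for planning the next trial, that noise goes straight into the result.

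The drop rule raises a different problem. Once the interaction is removed, the condition coefficient describes the arms over baseline and follow-up together. Baseline precedes the intervention, so this does not measure what the BI did. The SAP does not say whether the interaction estimate and its CI are still reported in that case.

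**Working it through.** **Inputs**
- Waves: two. Protocol D.5.b: "We plan a 2 (interventions) x 2 (baseline, follow-up) design".
- Sample: Protocol D.5.d: "We will recruit 50 women using screening, eligibility, recruitment, and consent procedures described in D.1.c". The basis in D.5.c is a guideline, "which recommend 15-30 per cell for Phase IB research". No formula-based figure exists to reproduce. 50/2 = 25 per arm lies inside the guideline if allocation is 1:1; the ratio is not stated.
- Follow-up: at least 80% expected (D.5.i), so 0.8 × 50 = 40 women, about 20 per arm.
- Baseline-to-follow-up correlation rho: not in the documents. Assumed 0.3 to 0.7, with 0 to 0.9 also shown.
- Ratio k of baseline SD to follow-up SD: not in the documents. Assumed 1, with 0.8 and 1.2 also shown.
- Confidence level: 95% assumed; it cancels from the large-sample width ratio.

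**Step 1: efficiency (n per arm, equal SDs)**
- Difference in change: Var = 2 × SD² × 2(1 − rho)/n.
- Baseline-adjusted: Var = 2 × SD² × (1 − rho²)/n.
- Variance ratio = (1 + rho)/2, so the share of CI width saved = 1 − sqrt((1 + rho)/2).

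Example at rho 0.5, n = 25: 1.96 × sqrt(2 × 2 × 0.5/25) = 0.554 SD against 1.96 × sqrt(2 × 0.75/25) = 0.480 SD.

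The last two columns charge the baseline covariate for its coefficient: a t quantile with one fewer degree of freedom and a variance factor 1 + 1/(N − 5), where N is the total analysed.

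| rho | Half-width, change (SD) | Half-width, adjusted (SD) | Saved | Saved after cost, 25 per arm | Saved after cost, 20 per arm |
|---|---|---|---|---|---|
| 0.3 | 0.656 | 0.529 | 19.4% | 18.4% | 18.2% |
| 0.5 | 0.554 | 0.480 | 13.4% | 12.4% | 12.1% |
| 0.7 | 0.429 | 0.396 | 7.8% | 6.7% | 6.4% |

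The extremes, 6.4% and 19.4%, give the range of about 6 to 19%.

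**Step 2: sensitivity to the assumptions**
- Equal SDs, large-sample: 29.3% at rho 0, 5.1% at rho 0.8, 2.5% at rho 0.9 (about 1% after the coefficient cost).
- Unequal SDs: saved = 1 − sqrt((1 − rho²)/(1 + k² − 2·rho·k)). For rho 0.3, 0.5 and 0.7, k = 0.8 gives 11.4%, 5.5% and 1.0%; k = 1.2 gives 27.3%, 22.2% and 18.1%.

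**Step 3: does this carry over to GEE and counts?** A simulation used 25 per arm, 600 trials per setting, an exchangeable working correlation and over-dispersed counts with mean 8 (assumed). It compared the SD of the interaction estimate with that of two alternatives. Reductions are given as baseline-covariate model / common-baseline GEE:
- Linear, full follow-up: 19/19% at rho 0.3, 11/12% at 0.5, 7/9% at 0.7.
- Linear, 80% follow-up: 16/17% at 0.3, 11/12% at 0.5.
- Counts, full follow-up: 22/22% at latent rho 0.3, 12/12% at 0.5.
- Counts, 80% follow-up: 18/18% at 0.3, 10/11% at 0.5.

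Each simulated SD carries a Monte Carlo error of about 3%. The last three settings were not simulated at rho 0.7. Where run, the results agree with Step 1.

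**Step 4: chance baseline gaps.** At 25 per arm the SE of a baseline difference is sqrt(2/25) = 0.283 SD. A gap of at least 0.4 SD (z = 0.4/0.283 = 1.41) occurs about 16% of the time per outcome. At rho 0.5 the difference in change over-corrects it by (1 − 0.5) × 0.4 = 0.2 SD.

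**Step 5: the drop rule.** In the linear case with full follow-up, the condition term without the interaction equals (baseline difference + 3-month difference)/2. Its expected value is half the 3-month effect. The rule would often apply: at rho 0.5, 25 per arm and a true effect of 0.3 SD (all assumed), the SE is sqrt(0.08) = 0.283, z = 0.3/0.283 = 1.06, and power is about 18%.

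**The case against.** The interaction is the hypothesis in both documents, it is valid, and the protocol accepts wide intervals. At rho 0.5 the gain is 0.554 to 0.480 SD, which is modest. The chance shift of 0.2 SD in Step 4 sits well inside the interval. Women are selected on baseline drinking and sexual risk (Protocol D.1.c), so unequal SDs are plausible in either direction, and with k = 0.8 little may be gained. The SAP is in the past tense and already reports a likelihood-ratio result (chi-square 60.76), so any change of model is post hoc. A plain model of the 3-month outcome on baseline would also drop women without follow-up, up to about 10 of 50, although the SAP commits to using all women.

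Most of this stands. It limits the size of the point and shapes the remedy: a common-baseline GEE keeps the women with baseline data only. It does not answer the drop rule, which replaces the hypothesised contrast with a different quantity in the outcomes where the interaction is not significant.

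A reader might infer that the SAP's estimate is biased. It is not: the interaction is unbiased over randomisation, and the shift in Step 4 is conditional on a chance gap.

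**Conclusion.** The point holds for the six GEE outcomes and has two parts. Where the interaction is kept, the BI effect is valid but less precise than the collected data allow: about 6 to 19% of CI width, conditional on rho of 0.3 to 0.7, similar SDs and 1:1 allocation. Where the interaction is dropped, the condition term that remains is not a 3-month effect. That part depends on none of those assumed values.

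A reader might go further and take the percentage as a known loss, recoverable at no cost, in every model. The documents do not support this. They give neither rho nor the SDs, and under the alternatives in Step 2 the gain runs from about 1% to 29%. A baseline covariate costs about one percentage point at this sample size. The figure does not extend to condomless sex, whose baseline handling is not described.

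**What to change.** For each GEE outcome, report one 3-month BI effect with its CI, whatever the significance of the interaction. Obtain it from the existing GEE with time, time-by-condition and age, but no condition main effect, so that the arms share a baseline mean. Use an exchangeable or unstructured working correlation; under independence the model reduces, in the linear case and leaving age aside, to a comparison of follow-up means and the baseline information is lost. Use a robust SE with a small-sample correction, given 40 to 50 women.

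Beside it, show two sensitivity analyses: the 3-month outcome adjusted for its own baseline value (log(baseline + 1) for counts) and age, and the SAP's interaction model. Label the rerun post hoc.

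State one assumption. Protocol D.5.b lists randomisation before the baseline assessment, so a common baseline mean requires that allocation did not affect baseline answers. If it did, the difference in change would also be distorted.

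Cost: a paragraph of SAP wording and a rerun of the models, plus the one percentage point of precision in the baseline-covariate sensitivity analysis. Protocol Table 2 schedules the alcohol, consequence and partner measures at both visits, so no new data are needed.

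### For the GEE outcomes, the age main effect does not adjust the time-by-condition effect among women seen at both visits; only an age-by-time term would

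*SAP*

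**What the plan says.** The SAP (Data Analyses Plan) states the efficacy hypothesis as a difference in change: "We hypothesized an intervention-by-time interaction such that participants in the BI, but not the control, condition would reduce alcohol use". All analyses contain time (baseline vs. follow-up), condition, "and the time-by-condition interaction controlling for age". Age is the only covariate named, no age-by-time term is described, and no reason for choosing age is given.

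The models differ by outcome. Count outcomes "were analyzed using a Poisson distribution unless otherwise indicated" within GEE. For consequences, "Alcohol consequences were analyzed using linear models". For condomless sex the GEE could not be fitted: "Instead, a zero-inflated negative binomial model was chosen". The SAP names neither the working correlation nor the type of SE.

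Two further rules matter here. On the analysis set: "We used an intent-to-treat approach such that data from all women were used". On model reduction: "When interactions were not significant, models were run without the interaction terms".

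The protocol plans two assessments, at baseline and 3 months (D.5.b), in 50 women (D.5.c) aged 18 to 29 (D.1.c). It expects at least 80% to return (D.5.i). Its own efficacy analysis, a repeated measures ANOVA (D.5.i), names no covariate.

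**The concern.** A covariate adjusts a treatment effect only if it enters the contrast that estimates that effect. Here the contrast is change within women, compared between arms. Age hardly moves in 3 months, so a single age coefficient shifts both of a woman's fitted values alike and drops out of her change.

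A reader told that all models control for age would naturally take the interaction as age-adjusted. If the arms happened to differ in age, and change over 3 months depended on age, part of the estimated BI effect would be an age effect that the model leaves in place. Protocol D.5.j puts the emphasis on effect sizes and confidence intervals rather than significance tests. What those estimates are adjusted for therefore matters even in an unpowered pilot.

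**Working it through.** The documents give no figure on this point to reproduce, so the check is algebra followed by simulation.

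**Inputs.** From the SAP: the model terms, Poisson and linear GEE, all women analysed. From the protocol: 50 women, two visits, at least 80% return, so up to 50 − 0.80 × 50 = 10 women with baseline only. Assumed: log link for Poisson, 25 women per arm, age fixed at its baseline value.

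**Step 1: point estimate, complete pairs.** In arm g, woman i has fitted means m_i at baseline and m_i × r_g at follow-up; age enters m_i only. With the four arm-by-visit cells saturated, the GEE score equations force fitted cell totals to equal observed totals. This holds under independence and under exchangeable correlation, because the weighting matrix is the same for every woman in an arm. With two visits, an unstructured correlation is the same as an exchangeable one. Hence

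- Poisson: log r_g = log(Σy₂ / Σy₁) in arm g
- linear: change in arm g = mean(y₂ − y₁)

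The interaction is the difference between arms in these quantities. The age coefficient appears in neither.

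**Step 2: robust SE.** In the Poisson case, woman i contributes y_i2/Σy₂ − y_i1/Σy₁ to the sandwich variance of log r_g. Her fitted value is the same share of the arm total at both visits, so the age part cancels here too. The linear case works in the same way.

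**Step 3: numerical confirmation.** GEEs were fitted with and without age to 60 simulated trials per setting (25 + 25 women; assumed 2-year age imbalance; assumed age slope −0.08 on the log scale). With complete pairs, adding age changed the interaction by at most 1e-15 (Poisson) and 4e-15 (linear), and the robust SE by at most 4e-15, under both correlations. Model-based SEs did move (median ratios 0.964 to 1.060).

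**Step 4: where age does act.**

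| Route | Change on adding age |
|---|---|
| Interaction, 5 to 10 of 50 women with baseline only, exchangeable | median 0.03 to 0.04 SE |
| Same, independence | median 0.09 to 0.16 SE; largest single shift 0.95 SE |
| Interaction dropped, complete pairs, Poisson condition coefficient | median about 0.14 log units, maximum 0.40 |
| Interaction dropped, complete pairs, linear condition coefficient | median about 0.6 units, maximum 2.2 |
| Zero-inflated negative binomial interaction, complete pairs (39 converged fits) | median 0.07 SE, maximum 0.72 SE |
| Interaction, age updated in whole years at 3 months | median 0.03 SE, maximum 0.18 SE |

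The attrition rows assume that younger women are lost more often. A separate simulation with 10 of 50 lost gave medians of about 0.02 to 0.09 SE. These sizes depend on the assumptions; the exact zero in steps 1 to 3 does not.

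**Step 5: what stays unadjusted.** If log change varies by δ per year of age and the arms differ by Δ years, the interaction is shifted by about δ × Δ. Three assumed scenarios:

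- δ = −0.05, Δ = 2: expected shift −0.05 × 2 = −0.10. The mean interaction was −0.196 with no age term, −0.196 with the age main effect and −0.100 with age-by-time. The gap is 0.096, or rate ratios of exp(−0.196) = 0.82 against exp(−0.100) = 0.90.
- Δ about 1.5, milder dependence of change on age: 0.096 (SE 0.173) with or without the age main effect; 0.108 and 0.116 with age-by-time. The shift is 0.012 to 0.020, and 0.012/0.173 to 0.020/0.173 is about 0.07 to 0.11 SE.
- A further scenario gave roughly 0.2 SE, with almost no change in the SE.

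For scale, if the SD of age is 3 years (assumed), the SD of a chance difference in mean age is 3 × √(1/25 + 1/25) = 0.85 years. Imbalances of 1.5 and 2 years are then 1.8 and 2.4 such SDs, so these scenarios lie toward the unfavourable end.

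**The case against.** A reader might infer that the age adjustment in this SAP corrects nothing at all. The documents do not support that. The SAP analyses all women, and the protocol allows for up to about 10 without follow-up, so age can enter the interaction through incomplete pairs. Models are refitted when the interaction is not significant, which is likely in a trial that disclaims power, and age then moves the condition coefficient. Condomless sex is not analysed by GEE, and there the invariance is only approximate. All three stand. None makes the age main effect an adjustment of the hypothesised effect among women seen twice. In particular, the refitted condition coefficient averages baseline and follow-up, so it answers a different question.

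A reader might also infer that the BI estimates are biased by age. That is not supported either. Neither document reports an age imbalance or says that change depends on age. The age range is narrow and allocation is random. An age difference that shifts outcome level equally at both visits already cancels from the interaction, so that part needs no correction.

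Two technical limits also stand. Protocol Table 2 lists age at baseline and at 3 months, so exactness requires age to be held at its baseline value. The statement about precision concerns the robust SE, and the SAP does not say which type was used.

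**Conclusion.** The point holds for the Poisson and linear GEE outcomes. Among women with both visits, the age main effect leaves the time-by-condition estimate and its robust SE exactly as they would be without age. This rests on one age value per woman, a log or identity link, and a working correlation shared by all women; it does not depend on any simulated value.

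The practical size is unknown, because the documents give neither the age imbalance nor the relation of age to change. The assumed scenarios gave shifts of about 0.01 to 0.10 on the log scale. This is a mismatch between the stated adjustment and the effect it is attached to, worth correcting because it is cheap. It is not evidence that the results are wrong.

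**What to change.** In the GEE models, use baseline age plus age-by-time, so that the adjustment reaches the interaction. The cost is one degree of freedom per model and a line of text. The SAP is written in the past tense and already reports a likelihood-ratio test and outlier counts. If the term is added after the data were seen, present it as a sensitivity analysis beside the model as specified. If it is not added, describe the interaction estimates as effectively unadjusted for age.

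In either case, state the purpose of the age term, that age is the baseline value, the working correlation and the type of SE.

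A model of the 3-month outcome adjusted for baseline and age would also let age act on the treatment contrast. It is an alternative with a different estimator, not an equivalent, and it would need a stated handling of women with baseline data only, whom the SAP includes.

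### Dropping the time-by-condition term when it is not significant discards the estimate of the intervention effect and leaves a diluted condition coefficient

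*SAP*

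**What the plan says.** The SAP (Data Analyses Plan) describes the efficacy models this way: "All analyses examined the impact of time (baseline vs. follow-up), intervention condition (control vs. BI), and the time-by-condition interaction controlling for age". Baseline is therefore an outcome measurement, not a covariate. Both documents place the intervention hypothesis in the interaction; protocol D.5.i expects "an intervention x time interaction for all outcomes". The SAP then adds: "When interactions were not significant, models were run without the interaction terms". It gives no significance threshold for this step. It also does not commit to reporting the interaction estimate, or any confidence interval, once the term has been removed.

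Three statements in protocol D.5 bear on this rule:
- D.5.b on sequence: "Women will be randomized, complete baseline, receive intervention (BI or brochure), post-survey (BI arm only), and 3-month follow-up".
- D.5.c on power: "We recognize that the trial is not adequately powered to detect between-group differences".
- D.5.j on purpose: "the focus of our analyses will not be on strict significance testing but on estimating effect sizes and CIs".

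**The concern.** Removing a non-significant interaction is a familiar way to make main effects easier to read, and it does little harm when the interaction is a side question. Here the interaction is the estimand. The follow-up contrast from the full model (condition plus interaction) would also estimate the effect, but it needs the same term. Once the term is gone, the condition coefficient mixes pre- and post-intervention differences. The time coefficient mixes the change that would have happened anyway, including regression to the mean, with part of the intervention effect.

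The pilot is meant to suggest effect sizes for a fully powered trial. Under this rule an interaction estimate stays in the final model only if it is large relative to its standard error, which selects exaggerated values. Otherwise a shrunken main effect takes its place. Either could mis-size the next trial.

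**Working it through.** **No figure to reproduce.** The documents give no power, alpha or target effect. The only check available is 50/2 = 25 per cell, which lies within the 15–30 cited in D.5.c.

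**Inputs from the documents.** 50 women (D.5.c, D.5.d); two time points (D.5.b); at least 80% expected at follow-up (D.5.i), so 25 × 0.8 = 20 per arm.

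**Assumed.** 1:1 allocation, two-sided 0.05 for dropping the term, and the effect sizes, correlations and dispersion stated below.

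**Step 1: what each coefficient estimates (linear, complete, balanced data).** Let D0 and D1 be the BI-minus-control differences at baseline and follow-up, δ the true effect and T the control-arm change. Randomisation gives E[D0] = 0, and E[D1] = δ.
- Interaction, full model: D1 − D0, expectation δ.
- Condition, reduced model: (D0 + D1)/2, expectation δ/2.
- Time, reduced model: expectation T + δ/2.

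Least squares on simulated balanced data with δ = −0.50 gave a reduced-model condition coefficient of −0.249, as the algebra predicts.

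**Step 2: the log-link case.** With equal arms, a Poisson model with independence working correlation, and age ignored, the reduced-model rate ratio equals the BI total over both visits divided by the control total. Assume a baseline mean of 9 drinks per week, a 20% fall in controls (to 7.2), 25 per arm at baseline and 20 at follow-up, and a true rate ratio of 0.75 (BI follow-up mean 5.4):
- BI total: 25 × 9 + 20 × 5.4 = 333.
- Control total: 25 × 9 + 20 × 7.2 = 369.
- Ratio: 333/369 = 0.902. Share of the true log effect: ln 0.902 / ln 0.75 = −0.103 / −0.288 = 0.36.

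The share is below one half because follow-up has fewer women and lower counts, so it carries less weight.

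**Step 3: how often the term goes (linear, SD 1).** The probability that the interaction is significant is Φ( d / [√(2(1−ρ)) · √(2/n)] − 1.96 ), with d the standardised effect and ρ the within-woman correlation. For n = 20, d = 0.5, ρ = 0.5: 0.5 / (1 × 0.316) − 1.96 = −0.38, and Φ = 0.35.

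| True d (ρ = 0.5) | Kept, 25 per arm | Kept, 20 per arm | Expected condition coefficient if dropped |
|---|---|---|---|
| 0.3 | 18% | 16% | 0.15 |
| 0.5 | 42% | 35% | 0.25 |
| 0.8 | 81% | 72% | 0.40 |

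At d = 0.5 and 20 per arm, letting ρ run from 0.3 to 0.7 gives 27% to 53% kept, so 47% to 73% dropped.

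**Step 4: both sides of the selection, by simulation.**
- Linear GEE, true effect 0.50, 20% dropout, 400 runs: the interaction averaged 0.51 in size overall, 0.79 when significant and 0.30 when not. The reduced-model condition coefficient averaged 0.21.
- Poisson GEE, robust standard errors, 3,000 trials per scenario, Step 2 assumptions plus correlation about 0.5 and over-dispersion about 8:

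| True rate ratio | Term dropped | Condition coefficient ÷ true log effect, when dropped | Interaction ÷ true log effect, when kept |
|---|---|---|---|
| 0.75 | 79% | 0.36 (rate ratio about 0.90) | 2.2 (rate ratio about 0.53) |
| 0.65 | 63% | 0.36 | 1.7 |

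**Step 5: sensitivity.**
- Independence and exchangeable working correlation, over-dispersion 3–8, 80% retention: dropped in 66–82% of trials at rate ratio 0.75 and 40–68% at 0.65; condition coefficient 28–37% of the truth; kept interactions 1.4–2.5 times the truth.
- A wider grid (over-dispersion 2–8, correlation 0.5–0.7, retention 80–90%, rate ratio 0.50–0.75, independence): dropped in 24–85%; condition coefficient 26–38%; kept interactions 1.2–2.7 times the truth.

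**The case against.** The strongest reply is that nothing is said to be withheld. The full model was fitted for every outcome, and the SAP says only that models were also run without the interaction. A report could still show the interaction estimate. That is fair as far as it goes, and if both were reported the selection harm would shrink. But the SAP makes no such commitment, the natural reading is that the reduced model is the final one, and its condition coefficient stays diluted either way.

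Other points stand as limits. The SAP states no alpha; 0.05 is the conventional reading. The factor of exactly one half needs complete, balanced linear data, and only one of the six primary outcomes listed for GEE is modelled linearly. The dispersion, mean and control trend are not in the documents, and the dropping rate moves widely with them. A truly large effect would often be kept: 81% of the time at d = 0.8 with 25 per arm. The SAP is in the past tense, so it records work done. Finally, this is a pilot whose feasibility and acceptability results are untouched. None of this makes the reduced-model coefficient an estimate of the intervention effect.

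**Conclusion.** The concern holds and needs correcting. That the reduced-model condition coefficient is diluted follows from the SAP's own model and the order of baseline and intervention; it needs no assumed effect size. The amount does rest on assumptions. It is one half in the balanced linear case, and roughly 26–38% of the true log effect in the Poisson settings examined when the term is dropped. Interactions that survive overstate the effect by about 1.2 to 2.7 times across the same settings. Under moderate true effects dropping is the likelier outcome, so for an underpowered pilot the rule would act often. It also conflicts with the protocol's stated preference for estimation over testing.

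**What to change.** Withdraw the rule that lets the P value choose the reported model. For each primary outcome, keep the time-by-condition term, or use a follow-up model adjusted for the baseline value, and report the rate ratio (or mean difference for alcohol consequences) with its 95% CI whatever the P value. Apply the same reporting to the condomless-sex model. If the no-interaction fits are kept as a record of what was run, label them supplementary, and do not present their condition or time coefficients as evidence about the intervention.

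The cost is a short SAP edit and a re-run of existing models; no new data are needed. The change adds no power, and the intervals will be wide, which protocol D.5.j already accepts.
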